### **11.4 Attribution of Adverse Events**

All adverse events will be further evaluated for attribution as per the following:

- Unrelated: Adverse event is clearly not related to the investigational agent.
- Unlikely: Adverse event is doubtfully related to the investigational agent.
- Possibly: Adverse event is possibly related to the investigational agent.
- Probably: Adverse event is probably related to the investigational agent.
- Definitely: Adverse event is definitely related to the investigational agent.

### **11.5 Plan for data collection and AE reporting**

Study outcomes, including success or failure of exstrophy closure, urinary continence, operative time, length of hospital stay, and a record of all peri-operative and post-operative complications, will be collected quarterly by IRB approved study staff from the patient’s medical record for 12 months post procedure.

Operative complications will be defined as complications that may be a direct effect of the quality of the operative procedure. Failure of exstrophy closure is defined as either a post-operative dehiscence, bladder prolapsed, or a vesicocutaneous fistula. These outcomes will be compared to previously established rates of success, complications, continence, etc.

Only those AE’s deemed as possibly, probably or definitely attributable to use of the investigational device will be collected and reported at the time of the annual IRB continuing renewal.

If a serious adverse event (SAE) occurs, the study investigator will complete and submit the Unanticipated Problem form or Problem/Event reporting mechanism via the eIRB. The investigator will also compile with urgent priority other relevant documentation (e.g., copies of test results,

hospital discharge summary, autopsy report, etc.). The IRB will be informed of all required SAE's within ten (10) days as per JHM IRB and institutional guidelines.

Serious adverse events will be reported to the FDA at the discretion of the principal investigator via the FDA Med Watch 3500 voluntary reporting mechanism.

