##### **b. Treatment Failure/Patient Removal**

This study does not involve any change to specific disease treatment, so treatment failure definition is not appropriate for this trial. A patient may be removed from the study based on the wishes of their parent/guardian or if a member of the designated group of faculty in charge of safety monitoring (outlined in section 11) feels that the safety of the patient is jeopardized by the new intervention. Studies show that as high as 63% of closures fail [15]. The designated faculty will work to determine if the treatment failures are a result of this designated intervention and if so patients will be withdrawn. Any data collected up to the date of patient/guardian withdrawal of consent will be kept and included in study analyses. Any patients removed from study will be replaced.

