## **9.2. Risks Specific to Research Activities**

Soft tissue distortion that occurs during surgery or inaccuracies during registration of the virtual diagnostic images described in section 6.5 may cause the virtual image to misrepresent the patient's actual anatomy. However, this poses minimal risk to the patient as the image guidance will only be used as a supplement to direct visual inspection of patient's anatomy by the surgeon and will not be used as the primary source for visual guidance into the operating field.

Another risk is the possibility that the external fixator pins described in section 6.5 may shift from their original placement while applying the VectorVision® 2-pin fixator. Though this risk is unlikely, if this were to happen corrective measures would be taken to restore the

external fixator pins back to their appropriate position prior to continuation of the procedure.

Just as with use of any computerized equipment, there is a risk of equipment malfunction that may result in an increase in operating time. Overall, known risks are rare, but these and any unanticipated problems will be medically managed as appropriate, and reported to the IRB and FDA promptly as per DSMP.

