## 11. Data and Safety Monitoring Plan

The research involves some risks to the participants. A group of designated faculty, that includes Pediatric Orthopedic Surgeon [name], Pediatric Anesthesiologist [name], and Adult Urologist [name] [name], will be involved in safety monitoring. These individuals will be notified promptly for any serious adverse events or deaths and will perform routine monitoring and oversight reviews of the research and postoperative outcomes to assess for trends or risks that were not previously identified. In the event of an adverse event, unanticipated problem, or a study deviation the IRB will be notified within 24-48 hours and the research will be halted pending review. Per the Johns Hopkins IRB policy 103.6b, "Unanticipated problems involving risks to participants or others" is defined as: The information is unexpected in terms of nature, severity, or frequency, given:

- a. The research procedures described in the protocol and informed consent document; and
- b. The characteristics of the subject population being studied; and
- c. The information indicates that participants or others are at greater risk of harm (including physical, psychological, economic, or social harm) than was previously known or recognized.

Also as per policy, the prompt reporting of unanticipated problems or events will occur as soon as possible after the PI learns of the event, but in all cases within 10 working days with the exception of death of a participant which must be reported within 3 working days.

Additionally, a team of designated faculty, including the PI's clinical fellow, the orthopedic surgeon ([name]), and the radiologist ([name]), will be present to monitor the patient during surgery. Standard safety monitoring by the anesthesiology team during surgery and post-operative nursing staff will monitor the patient for any safety concerns related to the surgery or immediate post-operative care.

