### 11.1 Adverse Events

An adverse event (AE) is defined as an unusual and undesirable symptom or sign that occurs in participants during the clinical study. Adverse events include those clinically significant laboratory values and test results, concomitant illness, accident, medical occurrence or worsening of existing medical condition that emerge during study participation.

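### Section 11 notifies the IRB and halts the research for any adverse event, but Section 11.5 collects only device-attributable AEs for annual reporting and mentions no halt; the two must be reconciled, and the AEs evaluated under 11.4 kept

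*Combined protocol and SAP*

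**What the plan says.** **Section 11 (Data and Safety Monitoring Plan).** "In the event of an adverse event, unanticipated problem, or a study deviation the IRB will be notified within 24-48 hours". The same sentence gives a further consequence of such an event: "the research will be halted pending review". Serious adverse events are named separately in the same paragraph, as events the designated faculty hear about promptly. The notice-and-halt sentence has no such qualifier.

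**Section 11.5.** The AE rule covers only events rated at least possibly "attributable to use of the investigational device will be collected and reported at the time of the annual IRB continuing renewal". SAEs go to the IRB "within ten (10) days as per JHM IRB and institutional guidelines". No halt is mentioned. The first paragraph of 11.5 separately collects all peri-operative and post-operative complications for 12 months, whatever their attribution.

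**Section 9.2.** After describing image misregistration, fixator pin shift and equipment malfunction, it says that "these and any unanticipated problems will be medically managed as appropriate, and reported to the IRB and FDA promptly as per DSMP".

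**FDA routes in the monitoring plan.** "Serious adverse events will be reported to the FDA at the discretion of the principal investigator" (11.5). Item a of 11.5 adds a route for deaths.

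**Sections 11.1, 11.2 and 11.4.** Section 11.1 opens by calling an AE an unusual and undesirable sign or symptom, then widens the term: "Adverse events include those clinically significant laboratory values and test results, concomitant illness, accident, medical occurrence or worsening of existing medical condition". Section 11.4 has all AEs evaluated on a five-level attribution scale that includes unrelated and unlikely. Section 11.2 says that severe, device-attributable AEs are recorded and followed until mild.

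**The concern.** A halt triggered by any AE cannot be applied consistently beside a rule that collects a subset of AEs for yearly reporting. Staff working from 11.5 would carry on after events that, under Section 11, stop the research. Staff working from Section 11 would stop for events that 11.5 does not ask them to collect.

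The second issue is the attribution record. Safety is part of the first primary objective (2.1a). The trial is unblinded with a single arm (4.1), and the principal investigator performs the closures (6.1c). Attribution is therefore a judgement made without a comparison group. If an AE is evaluated, called unrelated and not carried into the study data, that call can be checked only by returning to the charts.

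**Working it through.** The conflict is one of text, so the first step is to set the rules side by side by type of event.

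| Event | Section 11 | Section 11.5 | Can both be followed? |
|---|---|---|---|
| Non-serious AE, unrelated or unlikely | IRB notice in 24-48 hours; halt | Not collected as an AE; no report; no halt | No |
| Non-serious AE, at least possibly attributable | IRB notice in 24-48 hours; halt | Collected; reported at annual renewal; no halt mentioned | Notice: yes, early notice plus a yearly listing. Halt: no counterpart |
| SAE | IRB notice in 24-48 hours; halt | IRB within ten days; no halt mentioned | Notice: yes, ten days is an outer limit. Halt: no counterpart |

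**FDA reporting.** Section 9.2 defers to the monitoring plan, so it is not an independent timeline. But the stated FDA routes there are for SAEs, at the investigator's discretion, and for deaths. A non-serious device event, such as a pin shift that is corrected in theatre, has no FDA route in the plan to which 9.2 points.

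**Attribution record.** Events evaluated under 11.4: all AEs. Events collected as AEs under 11.5: the upper three attribution levels. The difference is the unrelated and unlikely classes. From that difference, remove what is captured elsewhere: all peri- and post-operative complications (4.3a, 8.1, 11.5), SAEs and deaths. What remains is non-serious events outside the complication record, for example an intercurrent illness or an accident. If the 11.2 sentence is a recording rule rather than a follow-up rule, mild and moderate attributable AEs are also in doubt. The text does not say which it is.

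**Illustration of the halt rule read literally.** The documents give no AE rate, so the risk p that a child has at least one triggering AE is assumed to be 1%, 5% or 10%, independently between children. Section 4.2 gives both 25 and 60 as subject numbers, so both are shown.

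P(at least one halt) = 1 - (1 - p)^N; expected number of children with a trigger = Np.

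| p | N = 25 | N = 60 |
|---|---|---|
| 1% | 1 - 0.99^25 = 22%; 0.25 children | 1 - 0.99^60 = 45%; 0.6 children |
| 5% | 1 - 0.95^25 = 72%; 1.25 children | 1 - 0.95^60 = 95%; 3 children |
| 10% | 1 - 0.90^25 = 93%; 2.5 children | 1 - 0.90^60 = 99.8%; 6 children |

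Study deviations and unanticipated problems trigger the same halt and are not counted. The contradiction does not depend on these figures.

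**The case against.** **The annual report may only be a summary.** Word order supports this: the restriction in 11.5 governs which AEs are collected, not when the IRB first hears of them. A reader might infer that an attributable AE stays unreported for up to a year. The documents do not establish that, because notice in 24-48 hours followed by a yearly listing satisfies both sections. This objection stands for timing. It does not answer the halt, nor the non-serious unrelated AE that Section 11 notifies and 11.5 does not collect.

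**Closure failure may not be a trigger.** Section 4.1b says "Studies show that as high as 63% of closures fail", and a reader might conclude that most children would trigger a halt. The documents do not support that count. Section 4.1b gives closure failures their own faculty review, an outcome expected that often is arguably not unusual in the sense of 11.1, and the cited study's title concerns late presentation and failed initial closure. The objection stands against the count. It leaves open whether a closure complication is an AE for the halt, since the second sentence of 11.1 is wide enough to include one.

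**Nothing need be discarded.** Section 11.6 retains all data derived from the study, including case report forms and AE reports, and 11.5 can be read as describing what is compiled for renewal. This stands in part: it would be wrong to say that the plan throws evaluations away. But 11.6 keeps what has been collected, and no section says that an evaluation of unrelated or unlikely enters the study data.

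**The filter is reasoned.** Section 11.2 points to the wide range of AEs after surgery of this extent. That is a fair reason to limit what is forwarded to the IRB. It is a weaker reason not to keep an evaluation that 11.4 already requires.

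**Conclusion.** The point holds, with limited scope. Sections 11 and 11.5 cannot both be followed for a non-serious AE rated unrelated or unlikely. For other AEs the reporting times are compatible, but the halt in Section 11 has no counterpart in 11.5. Section 9.2 refers to an FDA route that the monitoring plan does not provide for non-serious device events.

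The gap in the attribution record is real but narrow: non-serious events outside the complication record and, on one reading of 11.2, mild or moderate attributable AEs. It would go too far to infer that the safety outcomes are compromised. The all-cause complication outcomes, the SAE and death routes and the faculty reviews of postoperative outcomes do not depend on the 11.5 filter.

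The conclusion rests on the wording alone. The halt probabilities are illustrations on assumed risks; they show only that a literal any-AE halt would probably be met in practice unless AEs are very rare. The plan should be corrected because safety oversight depends on staff knowing which rule applies, but the main outcomes survive as they stand.

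**What to change.** 1. Reconcile the notice and halt in Section 11, the prompt reporting in 9.2 and the timelines in 11.5. State which events each IRB notice, halt and FDA route applies to, by seriousness and attribution. Say whether a closure complication, which already has its own faculty review in 4.1b, counts as an AE for the halt. This review does not choose the rule.
2. In 11.5, provide that the grade and attribution of every AE evaluated under 11.4 are kept in the study data. Apply the attribution filter only to what is forwarded at annual renewal.
3. Make the 11.2 sentence consistent with this by stating whether it governs recording or only follow-up of severe events.

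The cost is wording, plus modest extra abstraction for at most 60 children whose charts are already reviewed quarterly and whose AEs must already be evaluated. The downside is a higher AE count, made up mostly of events unrelated to the device.

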**a. Death of study participant**

As per JHM IRB policy 103.6bi, "*Organization Policy on Reporting Death of a JHM Research Participant*," if a study participant dies within 30 days from the date of the investigational stereotactic bladder exstrophy closure surgery, whether expected or unexpected, the PI will report the death to the IRB and FDA promptly. Death not related to a risk of participation that was listed in the protocol or consent document and was more likely than not caused by the research procedures/study intervention will be reported to the IRB and to the FDA no later than 3 working days of when the PI receives the report of death. Deaths considered 'expected' due to the nature of the participant's underlying disease or condition or identified as caused by a possible risk of the intervention as described in the protocol and informed consent will be reported to the IRB no later than 10 working days of when the PI receives the report of death.

Additionally, if the PI receives information of the death of a JHM former participant who did not complete the protocol for whatever reason (including voluntary withdrawal or removal by the PI) the PI will report to the IRB the former participant's death as part of the next Continuing Review application for IRB review.

## **11.6 Plan for Data Management**

The PI will review study data on a quarterly basis and ensure that study documents are monitored every six months for the duration of the study for data accuracy and completeness. The PI will maintain a file of human subjects' research project documents including (at a minimum) the following items:

- a. A copy of the original human subjects research application submitted to the JHM-IRB
- b. A copy of the JHM IRB approved consent form.
- c. The original of each consent form signed by each participant enrolled in the research.
- d. A copy of all correspondence with the IRB, FDA, and others as appropriate
- e. A copy of all data derived from the study (case report forms, computer data, adverse event reports, drug/device accountability records etc.)

## **12. Data Handling and Record Keeping**

Per John Hopkins IRB record retention guideline (Nov. 2008) for investigational device research, the PI will assure that all essential study documents will be maintained for a period of 2 years after the latter of the following two dates: The date on which the investigation is terminated or completed, or the date that the records are no longer required for purposes of supporting a premarket approval application or a notice of completion of a product development protocol.

